1.2 Rationale

The major clinical question is whether a VLED and structured weight management program can be instituted as effectively in primary care in Australia.

While previous guidelines have retained a 5-10% weight-loss target, the 2010 SIGN Obesity guideline, recognising changes in obesity prevalence and also recent evidence for more aggressive interventions, has set a new weight loss/maintenance target of >15-20% for those with BMI >35 kg/m² or >30 kg/m² with serious medical complications such as T2DM.²⁰ However, in routine diabetes care, few people achieve a weight loss of >15kg (or >15%). Although bariatric surgery is recommended for patients with T2DM and obesity by both the Australian Diabetes Management guidelines²² and the Australian Obesity Management Algorithm²³, there is little realistic prospect of its being offered to most such patients because of surgical and follow-up resource limitations. Furthermore, many patients will not agree to surgery. However, there is clear evidence that a combined medical program of diet, exercise and anti-obesity drugs can generate and maintain >15kg weight loss for many patients.²⁴

The DiRECT trial¹⁹ clearly demonstrated that a structured weight management program conducted in the primary care setting enabled people to lose weight and maintain weight loss for up to 2 years such that a substantial proportion of participants achieved remission of T2DM. Whether this model of care for weight loss and remission of T2DM is feasible, acceptable and translatable to an Australian primary care setting needs to be determined.

1.3 Study hypothesis

Losing weight using a structured weight management program, which includes an initial period of total diet replacement, followed by carefully managed food reintroduction and then weight loss maintenance, is a viable treatment for inducing remission of T2DM and can be implemented in a primary care setting where large numbers of overweight and obese people with T2DM are managed in the Australia.

2. STUDY OBJECTIVES

This research will establish whether it is possible to produce remission of T2DM and how sustainable this is over 5 years. Optimised weight management will be achieved using an LED, with the meal replacement Optifast, in routine Primary Care, where most T2DM is managed. The study will also assess quality of life and attitudes during the intervention.

- **The study endpoint is**
 - Remission of diabetes at 1 year (HbA1c <6.5%, 48 mmol/mol and off diabetes treatment for at least the preceding 2 months)

- **Secondary endpoints**
 - Weight change
 - Quality of Life
 - Physical Activity
 - Serum Lipids
 - Attitudes to the VLED
 - Effect of VLED on eating behaviour
 - Durability of diabetes remission

3. STUDY DESIGN

DiRECT-Aus is a translational study based on the active arm of the UK DiRECT trial, which demonstrated effectiveness in achieving remission of T2DM using a structured weight management program in primary care.

3.1 Study Population

250 patients will be recruited to the study from general practices within the following Primary Health Networks:

1. SNPHN Limited trading as Sydney North Health Network
2. WentWest Limited trading as Went West
3. SWSPHN Limited trading as South Western Sydney Primary Health Network
4. Healthy North Coast Limited trading as North Coast Primary Health Network
5. Western Health Alliance Limited trading as Western NSW Primary Health Network (WNSW PHN)

Participating GP patient lists will be screened to identify patients, aged 20-65 years diagnosed with T2DM within the previous 6 years, who would be potentially eligible to participate. GPs will review these lists and remove any patients they consider would be ineligible or unsuitable to approach.

3.2 Inclusion criteria

- Written informed consent
- Men and women aged 20-65 years, all ethnicities
- T2DM of duration 0-6 years (diagnosis based on Australian diagnostic criteria)
- HbA1c criteria at study entry:
 - 48 mmol/mol ($\geq 6.5\%$) **or**
 - HbA1c > 42 mmol/mol (6%), but < 48 mmol/mol (6.5%) if subject is taking blood glucose lowering medication(s)
- Body Mass Index (BMI) >27 kg/m²
- Women of childbearing potential must be ready and able to use highly effective methods of birth control that result in a low failure rate of less than 1% per year when used consistently and correctly, unless truly abstinent (as a lifestyle choice), in a committed relationship with a male who is medically sterile or exclusively same sex attracted.

3.3 Exclusion criteria

- Current insulin use
- HbA1c $\geq 10\%$ (86mmol/mol) at screening
- Weight loss of $>5\text{kg}$ within the last 6 months
- eGFR $\leq 45 \text{ ml/min/1.73}^2$ at screening
- Substance abuse
- History of active or untreated malignancy or in remission from a clinically significant malignancy for less than 5 years. Exceptions to this criterion include basal or squamous cell skin cancer, in situ carcinoma of the cervix or in situ prostatic cancer
- Myocardial infarction within previous 6 months
- Severe or unstable Heart Failure defined as equivalent to the New York Heart Association (NYHA):
 - Grade 3 - marked limitation of physical activity. Comfortable at rest, but less than ordinary activity causes fatigue, palpitation, or breathlessness, and
 - Grade 4 - unable to carry out any physical activity without discomfort. Symptoms of cardiac insufficiency at rest. If any physical activity is undertaken, discomfort is increased.
- Learning difficulties which in the opinion of the investigator prevent the subject providing informed consent and complying safely with the diet
- Use of weight loss agents or medications taken to primarily reduce weight (eg orlistat, lorcaserin, Qysmia, Contrave, GLP-1 receptor analogues, over the counter or herbal weight loss agents) within the past 3 months
- Have ever been diagnosed with and eating disorder or engaged in purging behaviour
- Pregnant/ considering pregnancy
- Patients with unstable mental illness
- People currently participating in another clinical research trial
- Allergy to Optifast or any of its ingredients

3.4 Identification of participants and consent

Potential participants will be identified by the GP either during routine care or from a search of practice records, performed either by the GP or practice staff and reviewed by the GP to identify patients who in the GP's opinion are appropriate for the study. The study will also be advertised via a study poster, brochure, and Information Pack available in participating GP practices. A study website

[www.diabetesnsw.com.au/directaus] accessible using a Quick Response (QR) code will be used to communicate information about the study to potential participants. The website will provide details including the purpose of the study, eligibility criteria, what is involved in participation, who is conducting the research, and access to a downloadable version of the Information Pack. The website will clearly state that participation in the study is optional and voluntary and will not affect their relationship with their GP or routine care. The website will also be used to communicate information to GPs in a restricted access section.

The QR code will be displayed on the poster and participant brochure. The poster, brochure, Information Pack and website will also display a toll free number monitored by researchers at Diabetes NSW & ACT which participants may use to obtain additional study information and undergo pre-screening for the study. Verbal consent will be obtained by researchers at Diabetes NSW & ACT to record personal contact information and outcome of pre-screening of potential participants who contact the study team using the toll free number in a recruitment database which will be password protected.

Patients identified during routine care

Patients identified during routine care as potentially eligible will have the opportunity to discuss the study with the GP. They will be provided with the Patient Information Statement (PIS) and encouraged to schedule a screening appointment by calling the practice if interested in participating. Verbal consent will be obtained to share the patient's contact details with researchers at Diabetes NSW & ACT for the purpose of recording recruitment activities and being contacted by Diabetes NSW & ACT regarding participation in the study. Reception staff at GP practices will be instructed to notify Diabetes NSW & ACT when any new screening appointments for the study are booked. Diabetes NSW & ACT will update the recruitment database accordingly. Diabetes NSW & ACT will periodically check if patients who expressed interest through their GP have made a screening appointment. GPs will be notified if a patient has not made an appointment and the GP or Diabetes NSW & ACT will contact the patient. Patients will be followed up until they express that they do not wish to participate or do not wish to be contacted further.

Patients identified from GP records

Patients identified as potentially eligible from a review of GP records will be contacted directly by the GP practice (via telephone) or, if the GP wishes to take a less active role, sent an invitation letter by the research team at Diabetes NSW & ACT.

Patients telephoned by the GP Practice

For patients contacted by the GP, a similar process to the above will be followed except the discussion between patient and GP will take place over the telephone and patients will be directed to the study website for access to written information about the study including the PIS. If interested in participating they will be encouraged to schedule a screening appointment by calling the practice and consent will be obtained as above for information to be shared with Diabetes NSW & ACT. As above, Diabetes NSW & ACT will periodically check if patients who expressed interest through their GP have made a screening appointment and if not, they will be followed up by the GP or Diabetes NSW & ACT.

Patients receiving invitation letter

For patients receiving the invitation letter, the letter will explain the purpose of the study and what is involved in participation, who is conducting the research and how they have been identified. The letter will clearly state that participation is optional and voluntary and will not affect their relationship with their GP or routine care. The PIS will be enclosed.

Interested participants will be asked to contact the research team at Diabetes NSW & ACT using a toll free number to discuss the study further. Patients who call the toll free number will be asked for verbal consent to undergo telephone pre-screening, which will involve answering questions regarding medical history and recent HbA1c results. Patients who appear eligible will be encouraged to contact their GP to make a screening appointment. Patients will be asked if they agree to having their personal contact details and outcome of pre-screening if conducted entered into a recruitment database which will be password protected and securely stored on the Diabetes NSW & ACT server. Patients who do not wish to undergo telephone pre-screening or who wish to discuss the study with their GP will be asked to make an appointment with their GP.

Reception staff at GP practices will be instructed to notify Diabetes NSW & ACT when any new screening appointments for the study are booked. Diabetes NSW & ACT will update the recruitment database accordingly. Diabetes NSW & ACT will periodically follow up patients who have expressed interest but have not yet made a screening appointment. Patients will be followed up until they express that they do not wish to participate or do not wish to be contacted further.

To maximise recruitment a non-response letter will be sent to patients who have not responded to the initial invitation, one month after the original invitation. This non-response letter will explain the purpose of the study and what is involved in participation, who is conducting the research and how

they have been identified. The letter will clearly state that participation is optional and voluntary and will not affect their relationship with their GP or routine care.

3.4.1 Non respondents

The age, sex, BMI and duration of diabetes of all patients from the GP lists who are identified as satisfying the recruitment criteria for DiRECT-Aus and who are invited to participate will be recorded using an anonymised list from each GP practice. Data will be compared for patients who agree to be in the study and those who decline to participate or do not respond to the invitation letter to determine differences, if any, between those who participate and those who do not. Such analyses are important to identify any recruitment bias and determine the representativeness of the study participants.

3.5 Withdrawal of subjects

Patients who withdraw from the study after commencement of participation in the study will continue to have data collected from their routine GP visits, unless they specifically withdraw consent for this. Data on weight and HbA1c recorded in GP notes within 3 months either side of the patients planned 12 months follow-up date will be used. Data analysis will use best available follow-up weights (from routine attendances) and end of study diabetes status for subjects who discontinue the formal weight management program.

Diet intolerance or poor-compliance will be recorded: these patients will be included in ITT analysis, but excluded in 'completers analyses'. The same procedures will be used to obtain the five year follow-up data.

4. Trial procedures

Practices will deliver an VLED phase followed by structured food reintroduction and long term weight loss maintenance. Training for the practice nurses/dietitians in VLED delivery, maintenance diet program and behaviour therapy will be provided by the Boden Collaboration, University of Sydney. Training for the practice nurses/dietitians in the maintenance diet program and behaviour therapy will be provided by Diabetes NSW & ACT. To increase access in regional areas, practices may deliver the intervention via telehealth but all participants will attend their GP practice for safety monitoring and collection of study data.

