TDR	Total Diet Replacement
GIG	Governance and implementation Group

STUDY SYNOPSIS

[figure not shown]
Title of Study:	Diabetes REmission Clinical Trial-Aus; DiRECT-Aus
Study Centre:	University of Sydney
Duration of Study:	Active intervention: 12 month per subject Follow up: 4 years after completion of active intervention
Primary Objective:	
To determine whether a program, designed to achieve remission of T2DM to normal glucose tolerance by substantial weight loss using a very low energy diet (VLED), can be effectively delivered within the routine primary care setting where most people with T2DM are managed in Australia.
 
The Diabetes Remission Clinical Trial (DiRECT) was a study funded by Diabetes UK that tested whether a low calorie-based weight management program, delivered in primary care could result in long term Type 2 diabetes remission. Diabetes UK, the University of Glasgow and Newcastle University have since developed the DiRECT principles, which set out the core elements of health intervention to have the best chance of replicating the outcomes of the DiRECT study.
 
This project intent is to replicate or better the remission results achieved in the UK DiRECT study for people with T2DM in the participating PHN regions and undertaking the intervention in general practice.

Secondary Objective:	To evaluate the attitudes of participants to the VLED program including acceptability, ease of use and perceived value.
Primary Endpoint:	% of participants achieving a non-diabetic HbA1c (<6.5%; <48 mmol/mol) at 12 months having ceased all diabetes medication for at least the preceding 2 months
Rationale:	Bariatric surgery can convert 70-80% of people with T2DM to the non-diabetic state. The DiRECT trial provided evidence that T2DM could also be reversed by a strict energy restricted diet, with 10-15kg weight loss. The present study will determine if the results of the DiRECT trial can be replicated in an Australian primary care setting and establish whether it is possible to produce remission of T2DM at 12 months and sustain it over 5 years. An VLED can be provided relatively cheaply in the primary care setting where obesity and T2DM are managed, using a total diet replacement (TDR), such as Optifast, which is readily available to the Australian general public. The study will also assess quality of life and attitudes of subjects during the intervention.

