4.2 Medications

4.2.1 Recording of medications

All medications will be recorded at screening on a CRF with information on start and stop date, dose, route, frequency and indication. The indication must match a medical history term or adverse event term. Participants will be prompted regarding changes to medications at each visit (including start date, stop date & dose changes). Changes will be recorded on the medications CRF.

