4.2.2 Management of blood glucose lowering and blood pressure lowering medications

Hypoglycaemic agents will be withdrawn on commencement of the VLED. Patients will be educated on detecting deteriorating glycaemia and glycaemia will be measured at each visit using capillary blood glucose measurement. HbA1c will also be measured 3-monthly. If capillary blood glucose is >15mmol/L or HbA1c >9% or >1% change in HbA1c from previous measurement, the GP will consider re-introducing oral hypoglycaemic medication. Recommencement of medication due to elevated blood glucose will be captured in the medication log and the reason noted.

Hyperglycaemia will also be recorded as an adverse event (see section 5).

Blood pressure will be measured at each visit during the first 12 months of the study. Subjects will be asked about symptoms of postural hypotension. If blood pressure is <110/60 mmHg, blood pressure medication will be reviewed and the medication will either be withdrawn or the dose reduced. If blood pressure is >140/90, prescription of blood pressure lowering medication will be considered by the GP.

All changes to blood glucose lowering and blood pressure lowering medications will be recorded on the medications CRF.

Other medications will be maintained, and their continued need and dosage reviewed as part of routine care.

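### For participants who withdraw, Section 3.5 names no data source for the drug-free half of the remission endpoint, so remission could be misclassified

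*Protocol*

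**What the plan says.** **Endpoint.** The synopsis defines the primary endpoint as a 12-month HbA1c below 6.5% in a participant "having ceased all diabetes medication for at least the preceding 2 months". Section 2 repeats the second condition as "off diabetes treatment for at least the preceding 2 months", and Section 4.5.1 also requires it. None of the three makes an exception for people who withdraw.

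**After withdrawal.** Section 3.5 makes three statements in sequence:
- Withdrawn patients "will continue to have data collected from their routine GP visits, unless they specifically withdraw consent for this". No items are listed.
- The follow-up values to be used are "Data on weight and HbA1c recorded in GP notes within 3 months either side of the patients planned 12 months follow-up date".
- The analysis uses the best available weights and "end of study diabetes status for subjects who discontinue the formal weight management program". How that status is determined is not described.

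The section then applies the same procedures to the five-year data.

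**Medication recording.** Under Section 4.2.1, "Participants will be prompted regarding changes to medications at each visit", and changes go on the medications CRF. Under Section 4.2.2, "Hypoglycaemic agents will be withdrawn on commencement of the VLED".

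**Analysis rule.** The synopsis and Section 6 carry the last observed weight and diabetes status forward for those who discontinue the program.

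**The concern.** The endpoint has two parts, and the sentence fixing the GP-note data for withdrawn participants supplies only one of them. These participants return to usual care, where their GP may restart glucose-lowering treatment. A GP-note HbA1c below 6.5% may then reflect drug treatment, and the named items cannot tell that apart from drug-free remission.

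The study has one arm, and its main aim, in Section 6, is to learn whether the program works as well as in the UK trial, where Section 1.1 gives 46% remission at 12 months. No control group would carry the same misclassification and offset it. Which items are taken from GP notes is also a data-collection rule. A statistical analysis plan can say how to classify remission, but it cannot use prescriptions that were never extracted.

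**Working it through.** The protocol states no figure that this point could reproduce. The check is a comparison of passages, followed by an illustration of size.

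**1. Source of each part of the endpoint**

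| Part | Participant still attending | Withdrawn participant |
|---|---|---|
| HbA1c < 6.5% | Week 52 blood test (Section 4.4, Table 1) | GP notes, within 3 months of month 12 (Section 3.5) |
| Off diabetes drugs ≥ 2 months | Medications CRF, prompted at visits (Section 4.2.1) | No item named |

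**2. What the last medication record shows.** Drugs are stopped at week 0. Unless they were restarted before the participant left, the last visit-based entry shows them as stopped. If that entry is carried to month 12, it favours remission.

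**3. Is the scenario possible here?** Yes. Section 3.2 admits people with HbA1c above 6% and below 6.5% who take glucose-lowering drugs, so the protocol itself recognises treated values under the endpoint threshold.

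**4. A worked case (hypothetical).** A participant enters with HbA1c of at least 6.5%, leaves at week 8, restarts tablets at week 16, and has a GP-note HbA1c of 6.2% at month 12.
- *Named Section 3.5 items with the last CRF entry:* 6.2% < 6.5%, and the last record shows drugs stopped. Both parts would appear to be met.
- *Last observation carried forward:* Table 1 has no HbA1c between screening and week 13, so the last study value is the screening one, at or above 6.5%. Not in remission.

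The two rules give opposite answers. For a later leaver, carrying forward does not close the gap either. Someone with HbA1c below 6.5% at week 13 and off drugs since week 0 has been drug-free for 13 weeks, which is over two months. If they then leave and restart drugs, the carried-forward status is still remission.

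**5. Which two months?** The window runs from month 12 − 3 = 9 to month 12 + 3 = 15.

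| HbA1c taken at | Two months before the HbA1c | Two months before month 12 |
|---|---|---|
| Month 9 | Months 7–9 | Months 10–12 (starts after the blood test) |
| Month 15 | Months 13–15 | Months 10–12 (ends 3 months before the blood test) |

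Section 3.5 does not say which period applies.

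**6. Illustrative size.** N = 250 is from the synopsis. Let w be the share who withdraw and m the share of those who are on drugs with HbA1c below 6.5%. The protocol gives neither, so both are assumptions.

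People affected = N × w × m; percentage points = 100 × w × m.
- w = 0.10, m = 0.05: 250 × 0.10 × 0.05 = 1.25 people; 0.5 points.
- w = 0.20, m = 0.10: 250 × 0.20 × 0.10 = 5 people; 2.0 points.
- w = 0.30, m = 0.20: 250 × 0.30 × 0.20 = 15 people; 6.0 points.

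Raising m to 0.30 with w = 0.30 gives 22.5 people, or 9 points, which shows how far the result follows the assumptions. All these figures also assume that every affected person is in fact classed as in remission.

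For scale, the 95% confidence half-width at 46% is 1.96 × √(0.46 × 0.54 / 250) = 0.062, or 6.2 points, ignoring clustering by practice.

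**The case against.** A reader might infer that withdrawn participants back on drugs will certainly be counted as in remission. The protocol does not support that. Nowhere does it judge them on HbA1c alone, and the drug-free condition stands in every statement of the endpoint. Section 3.5 also allows unspecified data from routine GP visits, which could include prescriptions, and it refers to diabetes status rather than to HbA1c. Its sentence on GP notes can be read as setting a date window for measurements rather than as a complete list of items.

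Other text points the same way. Section 4.2.2 wants all changes to glucose-lowering drugs on the medications CRF, without tying this to a visit. Section 4.6 makes the GP the person who decides on reintroduction. The synopsis says follow-up data continue when treatment stops. The carried-forward rule would usually class the week-8 leaver as not in remission. Nor must the bias run upwards: if unknown medication status were read as non-remission, true remissions would be lost. Finally, the classification of unconfirmed cases may be settled in the SAP, which was not available.

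Most of this stands, and it limits the point to possible misclassification. It does not remove the gap. Permission to collect GP data does not require prescriptions to be extracted, the visit-based prompt ends with the visits, and the one sentence that says which GP-note values are used leaves medication out. The conflict with the carried-forward rule adds to the uncertainty.

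**Conclusion.** The point holds in a limited form. On the data that Section 3.5 names, drug-free status after withdrawal cannot be confirmed, so a withdrawn participant on drugs with HbA1c below 6.5% could be misclassified as in remission. It does not follow that this will happen, or that the reported rate will be inflated by any given amount.

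The size is unknown. The range of 0.5 to 6.0 points is arithmetic on assumed rates and should not be quoted as an estimate of bias. It shows only that the effect could lie anywhere from negligible to about the sampling error of the primary result. The upward direction rests on a further assumption, that a stale record of stopped drugs is taken as current.

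The gap is still worth closing before GP records are extracted, because it concerns the primary endpoint, passes on to the five-year data, and may be hard to repair afterwards.

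**What to change.** In Section 3.5:
1. Change the retrieved items to weight, HbA1c and all glucose-lowering prescriptions with start and stop dates.
2. State that the two-month off-medication condition is judged on those records up to the date of the HbA1c used.
3. State that a participant counts as in remission only when both parts are confirmed.
4. Apply the same items to the five-year follow-up.
5. Reconcile the section with the carried-forward rule for diabetes status in the synopsis and Section 6, so that one rule decides the status of a participant who leaves.

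Reporting how many withdrawn participants had HbA1c below 6.5% but unconfirmed medication status would show how much item 3 matters.

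The cost is a short protocol edit and one more field on the extraction form, from notes already being opened for HbA1c. The remission rate may come out slightly lower, partly because some true remissions with incomplete prescribing records would not be counted.
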